non-VA provider appointment. Only those with upcoming visits with both providers in the next 6 months will be recruited. In our current work, we were able to use comparable methods to find veterans who had non-VA providers and we expect similar success in this study. To complete the study procedures, participants will be required to have access to a computer with internet, phone, and printer. At the time of enrollment, veterans will also be asked to complete a release of information so we may communicate with their non-VA provider and obtain a copy of their recent visit note, problem list, and medication list.

This pilot will be a randomized controlled trial comparing the CC intervention to usual care. This will allow for more conclusive determination of the impact of the intervention. In addition, results from this pilot can be compared to Dr.[name]'s pilot study examining unidirectional sharing of health information from the VA to non-VA providers only, to determine whether there was any additional benefit to bi-directional information sharing, the inclusion of the Co-Management Toolkit, and discussion of provider roles.

The study statistician will develop a computer program to implement randomization grouped in blocks to ensure equal distribution in study arms by age, gender, and race. The study coordinator will maintain randomization assignments in sealed envelopes to ensure that randomization and recruitment of specific patients is not influenced by future assignments. Veterans and providers in the usual care condition will complete all the same assessments, but will otherwise receive no aspects of the intervention.

Intervention Arm:

Veteran Intake Interview: In the intake interview, conducted by phone, veterans will be asked to confirm their medical conditions and list all their providers, including pharmacies, provide provider contact information, and to specify what roles and responsibilities are held by these providers (initial draft of form can be found in Appendix C). Veterans will also provide the dates of upcoming VA and non-VA provider visits. The results of the interview will be summarized. Veterans will also complete the Patient Perceptions of Integrated Care Survey(18, 19) with instructions to rate their experience in the past year. This initial assessment will serve as the baseline measure for patients' perceptions of CC.

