The Patient Perception of Integrated Care Survey (Appendix D) is a 33-item measure assessing perceived coordination within the care team, across care teams, between care teams and community resources, continuity, patient centeredness and shared responsibility. It has demonstrated internal consistency, discriminant validity, and goodness-of-fit.

Upon completion of the intake interview, study staff will send the veteran the training materials and link to online training videos that teach the veteran to use My HealtheVet to generate a CCD, share with their non-VA provider, and to compile information from non-VA providers that can be shared with VA providers through secure messaging. If the non-VA provider supports an online patient portal (e.g. Epic's My Chart), the staff will assist the veteran in using that tool if the veteran is amenable. A research assistant will contact the participant by phone to determine if they are having difficulties with the program and to provide any further assistance needed to bring success. In-person training and assistance will be offered when needed. In [name] current study, veterans have rarely needed assistance beyond the training materials provided. It appears that once veterans are made aware of the Blue Button Feature, the value of the feature in CC, and receive some guidance about how to go about generating a CCD, they can be fairly independent progressing through the whole process. More of a challenge has been finding veterans with scheduled visits within the next 6 months, though the original study did not target veterans with specific chronic or ambulatory care sensitive conditions. We expect that these patients will have more regular visits to manage their illness.

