Within My HealtheVet, a veteran can attach a file to their secure message and send that file to their VA health care team. If deemed clinically relevant, the VA health care team can then save that secure message in CPRS as a note and also save the file attachment In VistA Imaging. Phase 1 of this functionality was released in March 2014 and Phase 2 is scheduled for the 12.9 release of My HealtheVet in June 2014. Phase 2 will allow for a total of 4 file attachments per message with a maximum cumulative size of 6MB. The content included in the materials sent to the VA through secure messaging will be determined during the initial intake interview and will be shaped by perceived functions of health care team members. However, in general, patients will be asked to include a copy of their medication list, problem list, and most recent labs and most recent visit note.

We will instruct veterans to secure message non-VA health information to their PACT nurse care manager. The nurse care manager will then save the relevant information in CPRS and also notify other VA treatment team members, such as specialty care providers, of receipt of this information. We have discussed this process with ICVAHCS PACT leadership and they agree to promote this workflow.

Provider Visit: Veterans in both conditions will be followed in the study until they have had one VA and one non-VA provider visit. Those in the intervention arm will receive a reminder call one week prior to these visits

instructing them to bring hard copies of their list of providers and either their CCD from the VA, and informational aspects of the co-management toolkit (for non-VA providers) or most recent information from their non-VA care (for VA providers). Veterans will be asked to share this information with their providers and discuss whether or not the provider was aware of the other care and whether or not the provider concurs with the attributed roles. If discrepancies in expectations exist, the veteran will notify the PACT nurse care manager and work with the relevant stakeholders to start to clarify roles. Data about such discrepancies will be described in detail as part of the qualitative study of clarification of roles.

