Veterans in both study conditions will also be provided a postage paid envelope and brief evaluation forms to be completed by their providers and by the veteran. The patient post-visit questionnaire will include the Patient Perceptions of Integrated Care Survey. The provider forms include confirmation of receipt of information, its impact on care, provider satisfaction (Appendix E), and Gittell's Seven Item Measure of Relational Coordination designed for providers(20). (Appendix F) Gittell's 7-item measure of Relational Coordination assesses providers' perceptions of the frequency, timeliness, accuracy and problem-solving nature of communication, as well as relationships of shared goals, knowledge, and mutual respect. To facilitate participation, a waiver of signature of consent will be obtained from the IRB for providers.

The provider post-visit questionnaire will be comparable to the one currently used in the HSR&D study but additional questions will be added pertaining to the designation of provider roles, knowledge of and acceptability of CC agreements, and the usefulness of the Co-management Toolkit for non-VA provider questionnaires. The questionnaire will also include a section where the physician can indicate if he or she would be willing to complete a 15 minute audio-recorded qualitative interview about the medical visit. Although the proposed methods make some immediate demands on non-VA providers, response rate for the brief evaluation forms was high and 5 out of 21 providers agreed to be interviewed. Non-VA providers will also receive a small financial incentive for participation.

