Hypothesis 1: Patients in the intervention arm will have greater increase in the Perceptions of Integrated Care Survey score from baseline to the two provider visits when compared with usual care. This hypothesis will involve three dependent sample t-tests, assuming that Patient Perceptions of Integrated Care are distributed normally (if not normally distributed, analyses will use a Wilcoxon rank sum test). Specifically, we will examine differences between intervention and usual care patients with respect to the within-patient change between baseline perceptions and 1) perceptions after the first subsequent visit with a VA provider, 2) perceptions after the first subsequent visit with a non-VA provider, and 3) perceptions after subsequent VA and

non-VA provider visits averaged. Sub-analyses looking for differences between demographic groups based on age and gender will also be conducted.

Hypothesis 2: Providers in the interventional arm will have higher scores on the Relational Coordination Survey as compared to that of providers in usual care. The Relational Coordination survey will be completed by providers at each patient's first VA visit and first non-VA visit subsequent to baseline. Assuming coordination perceptions are normally distributed, analysis will use independent sample t-tests to evaluate differences in relational coordination perceptions between providers caring for patients in the treatment and usual care groups (alternatively, the Wilcoxon test may be used for non-normal measures). Differences in perceptions between usual care and treatment groups will be evaluated separately for VA providers and non-VA providers. These analyses assume that no two patient participants share a provider. If this assumption is not met, analyses will be adjusted to account for clustering within physician.

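### The post-visit integrated-care surveys have no stated recall period, yet Hypothesis 1 subtracts a past-year baseline from them

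*Combined protocol and SAP*

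**What the plan says.** The section on the Veteran Intake Interview has veterans complete the survey "with instructions to rate their experience in the past year", and gives that administration its role: "This initial assessment will serve as the baseline measure for patients' perceptions of CC". Training comes afterwards: "Upon completion of the intake interview, study staff will send the veteran the training materials and link to online training videos".

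The Provider Visit section repeats the instrument: "The patient post-visit questionnaire will include the Patient Perceptions of Integrated Care Survey". It gives no look-back period. Table 2 lists the survey at baseline, after the VA visit and after the non-VA visit, also without one.

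On timing, the Sample section says "Only those with upcoming visits with both providers in the next 6 months will be recruited". The Provider Visit section says "Veterans in both conditions will be followed in the study until they have had one VA and one non-VA provider visit", and sets no calendar limit.

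Against usual care, Hypothesis 1 expects that "Patients in the intervention arm will have greater increase in the Perceptions of Integrated Care Survey score from baseline to the two provider visits". For the analysis it says "we will examine differences between intervention and usual care patients with respect to the within-patient change between baseline perceptions and" three follow-up values: the score after the VA visit, the score after the non-VA visit, and the average of the two.

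**The concern.** A change score can be read only if one knows what period each rating covers. Here the first rating covers 12 months and the other two are undefined. There are two natural ways to fill the gap, and each causes a problem.

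- **Past-year wording reused.** The follow-up window overlaps the baseline window. Part of each follow-up score describes care received before any training, which pulls change towards zero in both arms and narrows the difference between them.
- **Survey tied to the visit.** A rating of one encounter is set against a rating of a year. The difference then contains a change of reference period as well as any change in care.

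If nothing is stated, staff or veterans may also apply different windows. This matters because the section on Outcome Assessments and Quantitative Analysis says the pilot is meant to supply an effect size and its variability for a later power calculation.

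**Working it through.** The plan gives no effect size, standard deviation, significance level or power, so there is no design figure to reproduce. The check takes each reading in turn.

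**Inputs from the plan.** Baseline recall is 12 months. Both visits are scheduled within 6 months of recruitment. Intake cannot precede the recruitment contact, so visits kept as scheduled fall at most about 6 months after baseline. Training starts after intake. The sample is 60 veterans.

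**Reading A: past-year wording reused.** For a survey t months after baseline, the share of the window before baseline is (12 − t)/12 and the share after it is t/12.

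| t (months) | Before baseline | After baseline |
|---|---|---|
| 1 | 11/12 = 92% | 8% |
| 3 | 9/12 = 75% | 25% |
| 5 | 7/12 = 58% | 42% |
| 6 | 6/12 = 50% | 50% |
| 8 (visit slips) | 4/12 = 33% | 67% |

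If visits were spread evenly over months 0 to 6 (assumption), the mean t is 3 and the mean share before baseline is 1 − 3/12 = 75%. Time spent on training after intake raises the pre-intervention share a little further.

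*Effect on the arm difference.* If respondents weight the year evenly (assumption), a true shift in experience after baseline is multiplied by t/12: a 1.0 SD shift appears as 0.08, 0.25 or 0.50 SD at months 1, 3 and 6. If they rate only the latest care, the multiplier is 1. The plausible range therefore runs from t/12 to 1, and the documents do not locate it.

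*Effect on later planning (illustration).* Take two-sided alpha 0.05, 80% power, SD fixed at 1 and a true standardised effect of 0.8, all assumed. Then n per arm = 2(1.960 + 0.842)²/d². Undiluted, d = 0.8 gives 25 per arm. Halved, d = 0.4 gives 99. Quartered, d = 0.2 gives 393. Required size scales with 1/d², so a later study would be planned about 4 or 16 times larger. Holding the SD fixed is a simplification: overlapping windows would also reduce the spread of change scores, so the standardised effect need not fall as far as t/12.

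**Reading B: survey tied to the visit.** The overlap is 0% and there is no dilution. Baseline covers a year and follow-up covers one encounter, so mean change within an arm cannot be read as improvement or decline. Randomisation still protects the comparison between arms, because the baseline means are equal in expectation and cancel. What is lost is the meaning of the change and some precision. With equal variances σ² and baseline-to-follow-up correlation ρ, the variance of raw change is 2(1 − ρ)σ², against (1 − ρ²)σ² after covariate adjustment. Their ratio is 2/(1 + ρ), which exceeds 1 for any ρ below 1 and grows as ρ falls; dissimilar reference periods could well lower ρ.

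**The case against.** The strongest reply is that the past-year instruction belongs to the intake survey alone. A reader might infer that the Hypothesis 1 change scores mostly re-rate care received before the intervention, or that the trial is too short for its instrument. The documents do not support that. They never say the past-year wording is reused, and Hypothesis 1 speaks of perceptions after each visit, which can be read as tied to the visit. The overview also describes the next visits as the things to be evaluated. The survey form is cited as Appendix D, which is not in the text available, and it may carry its own follow-up wording.

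Three further points stand. The shares of 50% or more need visits to occur by month 6, and follow-up has no stated cap. Usual-care participants complete the same assessments, so overlap would attenuate the comparison and would not by itself produce a spurious benefit. And this is a pilot for estimation, so a null test result is not the main worry.

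The reply does not remove the problem. The visit-tied reading avoids dilution but leaves a planned change score between unlike periods. Part of the instrument also concerns continuity and coordination across teams, which is not obviously a rating of one encounter.

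**Conclusion.** The concern holds in a conditional form. The recall period of the two post-visit surveys is unstated in the available text, and raw change is hard to interpret under either natural reading. Under reuse of the past-year wording, between 92% (month 1) and 50% (month 6) of the window precedes baseline, and less for later visits. The resulting attenuation lies between a factor of t/12, with even weighting, and none, with full weight on recent care. Under the visit-tied reading there is no attenuation, and the arm comparison remains valid, but within-patient change does not compare like with like. Which reading applies cannot be settled from the documents. The matter is worth correcting before data collection because it affects the quantity the pilot exists to estimate.

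**What to change.** 1. In the Provider Visit section, where the post-visit questionnaire is described, state that both post-visit surveys ask veterans in both arms to rate their care since the intake interview. Keep the past-year wording for baseline only, and make the form in Appendix D agree.
2. In Hypothesis 1, replace the t-tests on raw change by a comparison of arms on each post-visit score, and on their average, with the baseline score as covariate (ANCOVA). State that the contrast concerns experience since intake. The Wilcoxon fallback would need a counterpart, such as a rank-based ANCOVA.
3. Record the time from intake to each survey so that window length can be described by arm.

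**Cost.** One instruction line and a rewritten analysis paragraph; the sample, visits and randomisation are untouched, and the baseline score is already collected. There are three drawbacks. Raw within-patient change can no longer be read as like-for-like. The window differs in length between veterans. The second post-visit survey also covers the first visit, which blurs the separate VA and non-VA contrasts.

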Post Medical Visit Provider and Veteran Interviews: Providers and veterans who agree will be interviewed briefly by phone about their experience during the medical visit with a focus on CC. Willing veterans will be interviewed regardless of whether their provider does an interview. We will plan to conduct these interviews within one week of the scheduled appointment. If the non-VA provider agrees to complete a qualitative interview, a separate consent letter will be provided at that time prior to data collection detailing the information to be obtained. Again, a waiver of signature of consent will be utilized with clear instructions that by completing the audio recorded interview that he/she is providing consent to participate. The interview will address two main issues: the impact of the information exchange on the visit, and the acceptability and optimal design of a co-management care coordination agreement.

Outcome Assessments and Quantitative Analysis: The main outcomes of this study and when they will be collected are presented in Table 2. Though ordered in the table, we will not dictate what order the VA and non-VA provider appointments must occur – though this order will be noted in data collection. As this is a pilot study, we are conducting analyses to determine an estimate of effect size and expected variability to be used in a later power calculation for a larger experimental or quasi-experimental study.

Table 2: Study Assessments

Outcome			
Patient Perceptions of Integrated Care	Baseline	Post VA Visit	Post Non-VA Visit
Provider Relational Coordination Survey		Post VA Visit	Post Non-VA Visit
Medication Concordance- From Chart		Post VA Visit	Non-VA Visit
Medical Duplication- From Chart		Post VA Visit	Post Non-VA Visit

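### Hypothesis 1 names dependent-sample t-tests for what is a comparison of change scores between two independent randomised arms; the test name should be corrected

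*Combined protocol and SAP*

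**What the plan says.** All references are to the combined protocol and SAP, mainly the section Outcome Assessments and Quantitative Analysis.

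- **The hypothesis.** Hypothesis 1 predicts for the intervention arm a "greater increase in the Perceptions of Integrated Care Survey score from baseline to the two provider visits when compared with usual care".
- **The named test.** "This hypothesis will involve three dependent sample t-tests, assuming that Patient Perceptions of Integrated Care are distributed normally".
- **The fallback.** "if not normally distributed, analyses will use a Wilcoxon rank sum test".
- **The contrast.** The next sentence says "we will examine differences between intervention and usual care patients with respect to the within-patient change between baseline perceptions" and three follow-up values: after the first VA visit, after the first non-VA visit, and the average of the two.
- **The neighbouring hypothesis.** Hypothesis 2 is also a between-arm comparison. There, "analysis will use independent sample t-tests to evaluate differences in relational coordination perceptions between providers".
- **The purpose.** The opening paragraph of the section explains that, because this is a pilot, "we are conducting analyses to determine an estimate of effect size and expected variability to be used in a later power calculation".
- **The design.** The text before the Intervention Arm heading describes a randomised comparison with usual care. Blocks are used to balance age, gender and race, and no cross-arm matching of patients is described. It adds: "Veterans and providers in the usual care condition will complete all the same assessments".

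**The concern.** The named test and the stated contrast cannot both be carried out. A dependent-sample t-test takes two values from the same unit, or from a matched pair, and tests whether their mean difference is zero. The hypothesis instead compares mean change in two unrelated groups of patients.

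If the test name is followed literally, the natural result is a baseline-versus-visit test within the intervention arm. That does not answer the hypothesis, because it credits the intervention with any change that both arms share. Such change is plausible here: the baseline survey asks about the past year, while the follow-up surveys are completed after particular visits. The effect size passed to the later power calculation would then be a one-arm change and not a difference between arms.

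**Working it through.** The plan gives no alpha, power, effect size or SD for this outcome, so there is no figure to reproduce. The check has two parts.

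**1. The test against the text**

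| Element of the plan | Data structure it implies |
|---|---|
| Hypothesis 1, hypothesis sentence | Two independent arms |
| Hypothesis 1, named t-test | Paired values |
| Hypothesis 1, contrast sentence | Two independent arms, one change score per patient |
| Hypothesis 1, Wilcoxon rank sum fallback | Two independent samples (the paired counterpart is the signed rank test) |
| Hypothesis 2, named t-test | Two independent samples |
| Randomisation text | Two parallel arms, no matched pairs |

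Only the named t-test is out of line. A dependent-sample test could be applied in two ways: (a) baseline against visit within an arm, which is a different hypothesis; or (b) pairs formed across arms, which the design does not define.

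Once the change score is formed, the within-patient dependence has been used up. What remains is one number per patient in each of two independent groups.

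**2. What the literal reading could do (illustration only)**

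The plan gives 60 veterans in total. Everything else is assumed: equal arms (30 each if all contribute; 25 and 20 show smaller analysed numbers), two-sided 5% level, normally distributed change scores with SD 1, no treatment effect, and a shared mean change *m* in both arms.

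*Within-arm paired test.* The statistic has n − 1 degrees of freedom and noncentrality m√n. The rejection probability is P(|T| > t with 2.5% in the upper tail). For n = 30 and m = 0.5, the noncentrality is 0.5 × √30 = 2.74 on 29 degrees of freedom, and the rejection probability is 0.754.

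| n in the arm | m = 0 | m = 0.2 | m = 0.3 | m = 0.5 |
|---|---|---|---|---|
| 30 | 0.050 | 0.185 | 0.355 | 0.754 |
| 25 | 0.050 | 0.161 | 0.302 | 0.670 |
| 20 | 0.050 | 0.136 | 0.247 | 0.565 |

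*Two-sample t-test on change.* With n per arm it has 2n − 2 degrees of freedom (58 for n = 30). The shared change cancels, so the noncentrality is zero whatever *m* is. In simulation (100,000 replicates per setting, n = 20, 25 and 30, m = 0, 0.2, 0.3 and 0.5) it rejected 0.050 to 0.051 of the time.

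*Arbitrary cross-arm pairing.* In the same simulations this also rejected 0.050 to 0.051 of the time.

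The inflation therefore needs two things together: the within-arm reading and a change common to both arms.

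**The case against.** The best counter-argument is that the paragraph largely corrects itself. The hypothesis is comparative, the fallback is a two-sample test, and the contrast sentence states the between-arm difference in change for all three comparisons. An analyst would have to follow one adjective and disregard the signals around it. On this view, *dependent* is a loose reference to the within-patient change score and the rejection rates describe an analysis nobody intends. In addition, a pilot framed as estimation, with no stated alpha, is not well judged by false-positive rates.

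Much of this stands. The intended analysis can be recovered from the text, nothing suggests that the usual care data would go unused, and the rates above rest on assumed inputs. They show the direction of the harm and do not measure a risk specific to this trial.

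The power-calculation argument also has a limit. On the within-arm reading the mean carried forward is the wrong quantity, but the variability is not wrong in kind. A paired test uses the SD of within-patient change, which a two-sample design on change scores also needs. Only the pooling across arms is lost.

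None of this makes the name right. The section uses both *dependent* and *independent* for t-tests, so the word is not simply the authors' general term, and nothing elsewhere in the document corrects it. A plan should not depend on the analyst overriding the test that it names.

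**Conclusion.** The concern holds: Hypothesis 1 names the wrong test for one of the plan's main outcomes. It is an error of wording in the analysis plan and not a flaw in the design. It should be fixed, but the contrast sentence limits its practical effect.

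This conclusion rests only on the plan's own text. The illustrated size depends on the assumptions listed above and applies only to the within-arm reading: 14% to 75% false-positive findings over shared changes of 0.2 to 0.5 SD and 20 to 30 patients per arm, against about 5% for the two-sample test.

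**What to change.** In Hypothesis 1, replace the reference to dependent-sample tests with wording such as: *three independent (two-sample) t-tests comparing within-patient change from baseline between the intervention and usual care arms*. Keep the Wilcoxon rank sum test as the fallback, since it already matches. In the same sentence, attach the normality assumption to the change scores and not to the survey scores.

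State that the later power calculation will use the between-arm difference in mean change together with the pooled SD of the within-patient change scores. That SD should not be confused with the standard error of the estimated difference.

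The cost is a sentence or two of wording. No extra data collection is needed, because usual care veterans already complete the same baseline and post-visit surveys.

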In addition to the above considerations, this intervention targets the role of patient facing technologies in health information sharing. The availability of both patient and provider-facing technologies to improve health information exchange is rapidly evolving. The My HealtheVet Program Office anticipates that veterans will be able to send their CCD electronically directly from the MyHealtheVet website as of Fall/Winter 2014. In addition, [name] is working with local and national initiatives to promote provider-to-provider and state-based health information exchanges where the patient is not the intermediary. Though exciting, these technical developments are not currently available so they could not be incorporated into the design of this study. However, if they do become available during the study, the team and the Executive Committee will explore whether or not it would make sense to revise study methods to include them. The main focus of the assessments within the study is not whether a specific technology is used, but whether there is accurate and timely communication. At this level of analysis, we may be able to change the specific technology used, yet still determine the impact of health information sharing on the quality and efficiency of care provided.

Sample: Sixty dual use veterans who have a non-VA provider and who are not already using My HealtheVet for health information sharing will be recruited from the Iowa City VA Health Care System. Based on earlier research that identified criteria for optimal impact of CC(15-17), participants must have at least one of the following chronic illnesses or ambulatory care sensitive conditions: diabetes, chronic obstructive pulmonary disease, hypertension, congestive heart failure, angina, asthma, coronary artery disease, arthritis, gynecologic conditions, or cancer -as determined by medical record review. We will oversample women veterans so that the final sample contains at least 20 women veterans -30% of the total sample. Eligible veterans will be sent a recruitment letter with a postage paid return postcard asking them to indicate whether they have a non-VA provider or have ever used My HealtheVet for sharing health information with providers. When contacted, the research assistant will confirm inclusion criteria and request the date of the next scheduled VA-provider and

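### Hypothesis 1 rests on three comparisons of raw change with no lead result; one baseline-adjusted repeated-measures model would give one estimate, more precisely, from data already collected

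*Combined protocol and SAP*

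**What the plan says.** All references are to the combined protocol and SAP.

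- **Tests.** Hypothesis 1 expects a larger rise in the Patient Perceptions of Integrated Care score with the intervention. "This hypothesis will involve three dependent sample t-tests, assuming that Patient Perceptions of Integrated Care are distributed normally".
- **What is compared.** "we will examine differences between intervention and usual care patients with respect to the within-patient change between baseline perceptions" and, in turn, the score after the VA visit, the score after the non-VA visit, and the mean of those two. The fallback is also a two-group test: "if not normally distributed, analyses will use a Wilcoxon rank sum test". So the comparison is between arms, despite the word for paired tests in the first sentence.
- **What is not said.** Hypothesis 1 does not say which contrast leads, whether one or all must succeed, or what happens when a veteran has only one post-visit score. Baseline enters only by subtraction.
- **Data.** Baseline is taken at the telephone intake (Veteran Intake Interview), and usual care completes the same assessments (Sample). Post-visit forms go back in a postage-paid envelope (Provider Visit). No return rate for veterans is given.
- **Purpose.** Under Outcome Assessments and Quantitative Analysis: "we are conducting analyses to determine an estimate of effect size and expected variability to be used in a later power calculation".

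**The concern.** The pilot's product is an effect size and a variance. As written, Hypothesis 1 yields three of each, with none chosen to carry into the later power calculation. Where forms are missing, the three also come from different veterans.

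Each estimate is also noisier than it needs to be. Subtracting baseline removes the whole baseline score, noise included. Using baseline as a covariate removes only the part that predicts the outcome. In a randomised trial both target the same arm difference, so the choice affects precision. The averaged contrast may lose more, because a mean of two scores needs both surveys.

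At stake are the width of the interval around the pilot estimate and the size of the variance handed to the next study.

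**Working it through.** The plan gives no SD, correlation, alpha, power or return rate for this outcome, so there is no figure of its own to reproduce. What follows is an illustration over a range.

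**Inputs from the plan.** Total sample: "Sixty dual use veterans who have a non-VA provider". Allocation: blocks "to ensure equal distribution in study arms by age, gender, and race", with no ratio stated.

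**Assumptions.** 30 per arm; SD 1 at each time; baseline/post correlation r and post/post correlation s of (0.3, 0.5), (0.5, 0.6) and (0.7, 0.8); each post-visit survey returned independently with probability p.

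**Step 1: full return.** Variance per veteran for the averaged contrast:

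- raw change: Vc = (1+s)/2 + 1 − 2r
- baseline-adjusted: Va = (1+s)/2 − r²
- difference: Vc − Va = (1−r)², which is never negative

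| r, s | Vc | Va | Va/Vc | SE reduction, 1 − √(Va/Vc) |
|---|---|---|---|---|
| 0.3, 0.5 | 1.15 | 0.66 | 0.57 | 24% |
| 0.5, 0.6 | 0.80 | 0.55 | 0.69 | 17% |
| 0.7, 0.8 | 0.50 | 0.41 | 0.82 | 9% |

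A later trial of this outcome that adjusts for baseline but is sized on Vc would be too large by a factor Vc/Va: 1.74, 1.45 or 1.22.

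The single-visit contrasts gain too. Their variance ratio is (1−r²)/(2−2r) = (1+r)/2, which is 0.65, 0.75 or 0.85.

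**Step 2: incomplete return.** If the averaged contrast needs both surveys, 60p² veterans contribute. The model uses everyone with at least one, 60[1 − (1−p)²]. At p = 0.95, 0.90 and 0.80 that is about 54, 49 and 38 veterans against 60, 59 and 58.

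- raw change, both surveys: SE = √(2Vc / 30p²)
- model, all surveys: SE = 1/√{30[p²/(2Va) + p(1−p)/(1−r²)]}

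Worked case, r = 0.5, s = 0.6, p = 0.8:

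- raw change: √(1.60/19.2) = 0.289
- model: 1/√{30[0.64/1.10 + 0.16/0.75]} = 1/√23.9 = 0.205

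| r, s | p = 0.95 | p = 0.90 | p = 0.80 |
|---|---|---|---|
| 0.3, 0.5 | 0.291 to 0.213 (27%) | 0.308 to 0.216 (30%) | 0.346 to 0.225 (35%) |
| 0.5, 0.6 | 0.243 to 0.194 (20%) | 0.257 to 0.197 (23%) | 0.289 to 0.205 (29%) |
| 0.7, 0.8 | 0.192 to 0.167 (13%) | 0.203 to 0.169 (17%) | 0.228 to 0.175 (24%) |

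The model SE treats the covariance as known, so it is slightly optimistic at this sample size.

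**Step 3: where the gain comes from.** In the worked case, adjusting for baseline in complete pairs alone gives √(2 × 0.55/19.2) = 0.239. Adjustment therefore takes 0.289 to 0.239, and recovered surveys take 0.239 to 0.205. At high return, most of the gain is plain baseline adjustment.

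**Step 4: false positives.** Under no effect, the three correlated two-sided 5% tests were simulated at these correlations. At least one is significant in about 9-10% of trials. At least one is significant in the favourable direction in between 4% and 5%. All three are significant in between 1% and 2%.

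**The case against.** The plan's tests are not wrong. Comparing raw change between randomised arms is valid and matches the wording of the hypothesis, so the case is about efficiency. That stands.

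Veterans share different information with VA and non-VA providers, so separate contrasts have substance, and an average can hide an effect at one visit only. That also stands, and it is why the visit-specific estimates should be kept.

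A veteran with one survey still enters one of the single-visit contrasts, and recruitment is limited to veterans with both visits due within six months. Both are true. The complete-pair rule for the average is an inference, the natural one because no other rule is given. The gain at full return does not depend on it.

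Two stronger readings are tempting and are not supported.

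- **False claims nearly double.** A reader might infer this from three tests at 5%. It needs a rule that any one test, in either direction, counts as support. The plan states no such rule and no alpha. The hypothesis is directional, and the stated purpose is estimation.
- **Biased estimate.** A reader might infer bias if return depends on baseline score. If it does so equally in both arms, completers stay balanced. A simulation with about 61% of veterans returning both surveys and a constant effect gave a bias of 0.001-0.002 SD. Bias would need return to depend on baseline differently by arm, or an effect that varies with baseline. The documents give no evidence of either.

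**Conclusion.** The point holds as one of precision and of naming a lead estimate. Raw change is less precise than baseline adjustment at any correlation below 1, apart from the one degree of freedom spent on the covariate. For the averaged contrast the standard error falls by 9-24% with full return. It falls by 13-27%, 17-30% or 24-35% at 95%, 90% or 80% return if the average needs both surveys.

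These sizes rest on assumed correlations, equal SDs, independent survey return and a known covariance. The gain is small when the baseline correlation is high and nearly all forms come back. False-positive inflation is conditional and secondary in an estimation pilot, and no claim of bias is made.

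**What to change.** Replace the three t-tests with one linear mixed model of the two post-visit scores, with arm, visit type, arm-by-visit and baseline score as covariate. Include every randomised veteran with a baseline and at least one post-visit survey, in the assigned arm.

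Name the arm difference averaged over both visits as the lead Hypothesis 1 estimate. Report the baseline-adjusted VA and non-VA differences beside it, with 95% confidence intervals and SDs, so that the later study can size on whichever it adopts. If residuals are clearly non-normal, keep a rank-based or bootstrap check in place of the Wilcoxon fallback.

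This is a cheap improvement: a change of analysis wording and slightly more analysis work, with no new data. The costs are a missing-at-random assumption and that the two visit-specific contrasts become supporting results.
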